**Exclusion criteria**

- Failure to meet any of the above inclusion criteria.

**AMYOTROPHIC LATERAL SCLEROSIS (ALS)**

**Inclusion criteria**

- Signed written informed consent from the patient and/or legal representative (Appendix X);
- Age  $\geq 18$  years;
- Clinical diagnosis of motor neuron disease in patients referred to participating centers, as follows:

- Diagnosis of definite or probable ALS according to revised El Escorial criteria;
- EMG must demonstrate:
  - a) Active denervation (fibrillation potentials, positive sharp waves, complex fasciculations);
  - b) Chronic denervation (prolonged, often polyphasic motor unit potentials, reduced recruitment with high firing frequency at maximal effort);
  - c) Nerve conduction studies typically show reduced motor potential amplitude with preserved or minimally reduced motor conduction velocity, normal sensory conduction, and absence of conduction block;
- Transcranial magnetic stimulation (TMS) may demonstrate UMN involvement (reduced corticobulbar/spinal conduction velocity, decreased cortical motor neuron excitability);
- Neuroimaging and laboratory investigations must exclude compressive, infiltrative, or inflammatory conditions mimicking UMN/LMN signs.

**Exclusion criteria**

- Failure to meet any of the above inclusion criteria.

**PARKINSON'S DISEASE (PD)**

**Inclusion criteria**

- Signed written informed consent from the patient and/or legal representative (Appendix X);
- Age  $\geq 18$  years;
- Clinical diagnosis of PD according to revised MDS criteria, as follows:

- Predominant motor presentation with bradykinesia plus resting tremor and/or rigidity;
- MMSE  $>24$ , with preserved (MCI) or mildly impaired (mild dementia) instrumental daily living activities (CDR 0.5–1);
- Absence of significant neurological/systemic comorbidities or structural abnormalities indicative of other causes of cognitive impairment;
- Imaging findings:
  - a) Normal structural brain imaging;
  - b) Striatal DAT binding reduction on SPECT DAT-SCAN;
- Availability of longitudinal clinical assessments, including motor scales (e.g., UPDRS-III, Hoehn & Yahr), MMSE/MOCA, and daily living activities, for at least 24 months.

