- progression to dementia: MCI may evolve into more severe cognitive impairment with loss of functional independence, the hallmark of dementia. The annual progression rate from MCI to dementia is estimated at 10–15%, depending on underlying causes (notably AD and FTD) and individual risk factors.

Cognitive impairment may be restricted to a single domain (single-domain MCI) or involve multiple domains (multi-domain MCI). Patients can thus be classified into four clinical subtypes: (i) amnestic single-domain MCI (aMCI-SD), (ii) amnestic multi-domain MCI (aMCI-MD), (iii) non-amnestic single-domain MCI (naMCI-SD), and (iv) non-amnestic multi-domain MCI (naMCI-MD).

The MCI construct can further be staged clinically using the Clinical Dementia Rating (CDR) scale, a widely used instrument to assess cognitive decline and dementia severity over time. A CDR score of 0.5 is consistent with MCI, reflecting subtle cognitive changes exceeding normal aging (CDR = 0), but not yet meeting dementia criteria. Dementia is stratified according to severity and functional impairment into mild (CDR = 1), moderate (CDR = 2), severe (CDR = 3), very severe (CDR = 4), and terminal (CDR = 5).

Clinical characterization integrates laboratory and neuroimaging findings to guide clinicians in estimating risk and timing of progression. A central concept is that, by combining clinical subtypes with presumed etiologies, it may be possible to predict the specific type of dementia likely to emerge in patients with MCI. Current research is increasingly focused on genetic risk factors to identify individuals at higher risk of short-term progression.

**Parkinson's Disease (PD)** is the second most common neurodegenerative disorder in terms of prevalence and incidence. Its estimated prevalence is approximately 0.3% in the general population and 1–3% in individuals over 65 years of age.

Disease progression leads to degeneration of the nigrostriatal dopaminergic pathway, with marked loss of neurons in the substantia nigra pars compacta (SNpc) and subsequent dopamine (DA) depletion. Non-motor dysfunctions such as mild cognitive impairment (MCI), dementia, hyposmia, and gastrointestinal abnormalities frequently accompany disease progression.

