### Eligibility Criteria

Subjects will be enrolled only if they fulfill all inclusion criteria and none of the exclusion criteria for each neurodegenerative condition under investigation, as described below.

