### **DEMENTIA WITH LEWY BODIES (DLB)**

#### **Inclusion criteria**

- Signed written informed consent from the patient and/or legal representative (Appendix X);
- Age ≥18 years;
- Clinical diagnosis of DLB in patients referred to the participating centers, as follows:

- Predominantly non-amnestic cognitive impairment (visuospatial, dysexecutive, attentional) based on patient report or full neuropsychological assessment, plus characteristic clinical features according to current diagnostic criteria for DLB or MCI-LB;
- MMSE >24, with preserved (MCI) or mildly impaired (mild dementia) instrumental daily living activities (CDR 0.5–1);
- Absence of significant neurological/systemic comorbidities or structural abnormalities indicative of other causes of cognitive impairment;
- Supportive instrumental or imaging findings consistent with probable DLB, at least one of:
  - a) Polysomnographic confirmation of REM sleep behavior disorder without atonia;
  - b) Reduced striatal dopamine transporter uptake on SPECT/PET;
  - c) Abnormal cardiac [123I]-MIBG scintigraphy (reduced uptake);
- Availability of longitudinal clinical assessments, including MMSE and daily living activities, for at least 24 months.

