**Exclusion criteria**

- Failure to meet any of the above inclusion criteria.

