#### - Baseline visit and informed consent

The Investigator will invite patients to participate after verifying inclusion/exclusion criteria. Patients (or legal representatives in case of cognitive impairment) will receive detailed information on study aims, benefits, and potential risks, along with written information sheets and informed consent forms. Adequate time will be allowed for discussion with the general practitioner before consent. Patients will also be asked whether they agree to be re-contacted for future research studies.

Investigators at the Genoa and Milan centers are responsible for obtaining and archiving signed informed consent before any study-specific procedures.

#### - Visit 1

At this visit, informed consent will be obtained, and subjects will be enrolled with assignment of a pseudonymized code generated in REDCap using the Mainzelliste algorithm (PMID: 25656224). The algorithm processes identifying attributes (e.g., name, surname, date of birth) to generate a unique, anonymous personal identifier (PID), ensuring record linkage across multiple databases while tolerating spelling variations.

Peripheral blood (20–25 mL) will be collected for preparation of PBMCs, serum, and/or plasma, and urine will be collected for omics analyses. DNA will be extracted from whole blood, RNA preferably from PBMCs; saliva may be used as an alternative genetic source. Sampling will be integrated into routine clinical workflow.

Clinical and biological data will be collected at IRCCS Policlinico San Martino ([name]), Fondazione IRCCS Cà Granda ([name] [name]), and other participating centers.

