### Screening Failure

If it is determined that a subject is not eligible for enrollment despite having provided informed consent (e.g., due to an incorrect diagnosis), the patient will be classified as a screening failure. In such cases, all collected data will be deleted and any biological samples destroyed.

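### The PD entry criteria require CDR 0.5–1, so PD patients with normal cognition are ineligible as written, although the design and the PD analyses are framed for PD in general

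*Protocol*

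**What the plan says.** The PD inclusion list in Section 6 opens with a motor presentation. It then requires an MMSE above 24 "with preserved (MCI) or mildly impaired (mild dementia) instrumental daily living activities (CDR 0.5–1". The next line requires "Absence of significant neurological/systemic comorbidities or structural abnormalities indicative of other causes of cognitive impairment".

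The protocol explains the CDR scale in Section 1.1: "A CDR score of 0.5 is consistent with MCI, reflecting subtle cognitive changes exceeding normal aging (CDR = 0"; a score of 1 is mild dementia.

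Section 6 leaves no discretion over individual criteria. Under Eligibility Criteria it states "Subjects will be enrolled only if they fulfill all inclusion criteria and none of the exclusion criteria", and the only PD exclusion criterion is "Failure to meet any of the above inclusion criteria". Section 7.1 puts the check ahead of any contact about the study: "The Investigator will invite patients to participate after verifying inclusion/exclusion criteria".

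Other sections describe PD without a cognitive condition:

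- Section 3 names PD and degenerative parkinsonisms as one group and neurodegenerative cognitive disorders as another. The stage of MCI or dementia qualifies only the second.
- Section 5 (Secondary Objectives) plans transcriptomics in early-onset PD, and a rare-variant analysis of rapid against slow progressors defined by Hoehn & Yahr stage at 5 years.
- Section 7.4 (Statistical Approaches) reports results by disease, with PD and MCI as separate strata.

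**The concern.** The entry rule and the population described elsewhere do not fit. If sites apply the rule literally, every PD patient in the cohort has MCI or mild dementia at entry, yet nothing in the objectives or the analysis text tells a reader that the PD results are limited in that way.

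The loss cannot be repaired later. Criteria are checked before invitation, so cognitively normal PD patients would leave no data or samples for any analysis to use. If such a patient did consent and was then found ineligible, Section 8 (Screening Failure) applies: "In such cases, all collected data will be deleted and any biological samples destroyed". That is a residual case; the main loss is of patients who are never invited.

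Primary objective 2 correlates molecular alterations with clinical phenotype. In PD, normal cognition at entry would be absent from the phenotype range available for that work.

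There is also a practical risk. A site that reads the line strictly turns CDR 0 patients away, while a site that reads it loosely enrols them in breach of the criteria. With two centres, and more allowed to join, the PD group could differ by site.

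**Working it through.** The protocol states no formal power calculation, so there is no figure of its own to reproduce here. The check is one of logic and of setting sections side by side.

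**Step 1: does the exclusion follow from the text?**

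1. PD entry requires CDR in the range 0.5 to 1 (Section 6, PD list).
2. Normal aging is CDR 0, and 0.5 is MCI (Section 1.1).
3. All inclusion criteria must be met, and failing any one excludes (Section 6, Eligibility Criteria and PD exclusion criteria).
4. CDR 0 lies outside 0.5 to 1, so a PD patient at CDR 0 is ineligible.

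The reference to preserved daily activities does not change this. It is labelled as MCI and bounded by the same CDR range. The MMSE threshold alone would admit cognitively normal patients; the CDR range is what shuts them out.

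**Step 2: where might the line come from?**

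The DLB list in Section 6 contains "MMSE >24, with preserved (MCI) or mildly impaired (mild dementia) instrumental daily living activities (CDR 0.5–1", followed directly by the same comorbidity line that PD carries. The two consecutive lines are word for word the same in both lists. The second speaks of other causes of cognitive impairment, so it presupposes that impairment is present. That fits DLB, but sits oddly in a list that begins with a motor presentation. The ALS list has no CDR line, although Section 1.1 says that a considerable proportion of ALS patients have cognitive impairment. The pattern suggests carried-over text. It does not prove it.

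**Step 3: is the restriction stated as an aim, or ruled out, anywhere else?**

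| Place | What it says about cognition in PD |
|---|---|
| Section 1.1 | MCI and dementia often accompany progression; not a defining feature |
| Section 3 | MCI or dementia stage attached only to the cognitive disorders |
| Section 5, PD sub-studies | No cognitive condition |
| Section 7.4, reporting | PD and MCI as separate strata; no cognitive condition on PD |

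No section says that a cognitively impaired PD cohort is intended. No section says that CDR 0 patients will be enrolled.

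**Step 4: how large is the group that the criterion governs?**

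- Section 7.4: PD is about 30% of at least 1,000, so 0.30 × 1,000 = 300.
- PD plus parkinsonism in Section 7.4: (0.30 + 0.05) × 1,000 = 350.
- Section 5 gives more than 450 for PD and parkinsonism together.

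The two sections disagree on the combined group, so 300 is the Section 7.4 figure and not a settled one. The number of PD patients who would be excluded is the referred PD patients multiplied by the share at CDR 0. The protocol gives neither term, so that number cannot be computed.

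**The case against.** The best reply is that eligibility lists normally narrow the summary text. Section 3 does not repeat the MMSE and CDR limits for the dementias, and Section 7.4 projects AD at about 30% without mentioning the biomarker requirement; nobody would call those contradictions. Listing PD apart from dementia or MCI is labelling by primary diagnosis, and a PD patient with MCI still counts as PD. The PD list is also adapted to the disease: it has DAT imaging and motor scales, and it adds MoCA to the longitudinal assessments. The authors evidently thought about cognition in PD, so a deliberate restriction is possible.

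Much of this stands. The recruitment counts in Section 5, and the projection and strata in Section 7.4, differ from the criterion only by silence. A reader might infer that the protocol elsewhere promises to enrol cognitively normal PD patients; it does not. A reader might also take the matching lines as proof of a copying error; they are not.

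Two things survive. The literal exclusion is not in doubt. And Section 3 goes beyond silence: it states a cognitive stage and gives it to one group and not the other. If a restriction was intended, it changes what the PD sub-studies and PD results mean, and the protocol nowhere says so.

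**Conclusion.** The concern holds as a conflict between a restrictive entry criterion and descriptions of PD that carry no such restriction. As written, PD patients at CDR 0 cannot be enrolled, and PD conclusions would apply only to PD with MCI or mild dementia. This rests on the protocol's own meaning of CDR 0 and on its rule that every criterion binds; no assumed figure is used.

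The criterion governs about 300 patients on the Section 7.4 shares, subject to the disagreement with Section 5. How many would be excluded is unknown.

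Three stronger readings are not supported:

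- That PD recruitment will fall short. Without a referral count and the CDR 0 share, this cannot be shown.
- That the slow-progression group would be emptied. The protocol gives no link between cognitive status at entry and Hoehn & Yahr stage at 5 years.
- That the genetic comparisons fail. Variants can still be compared with controls in a cognitively restricted PD group; what changes is the population to which the result applies.

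The point should be settled early, because criteria are applied before invitation and the missing patients cannot be recovered by analysis.

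**What to change.** Reconcile the PD inclusion list in Section 6, both the CDR line and the companion line on other causes of cognitive impairment, with Section 3, the PD sub-studies in Section 5 and the reporting text in Section 7.4. There are two consistent ways to do it:

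- **If PD in general is intended:** amend both lines so that cognitively normal PD patients are not excluded. Changing the CDR line alone would leave a criterion that still presupposes impairment. The cost is a two-line eligibility amendment with no new assessment. The downside is a more heterogeneous PD group.
- **If the restriction is intended:** say so, and restate the PD sub-studies, the PD projection and the scope of PD conclusions as PD with MCI or mild dementia. The cost is a statement of intent and wording edits in Sections 3, 5 and 7.4. The downside is narrower PD conclusions.

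The choice is the sponsor's; the protocol does not settle which was meant.

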**Exclusion criteria**

- Failure to meet any of the above inclusion criteria.

## 7. LABORATORY PROCEDURES: GENETICS, OMICS, BIOMARKERS

### 7.1 Enrollment and Follow-up

#### - Patient selection

Eligible subjects will be identified during outpatient visits at IRCCS Policlinico San Martino (Genoa), Fondazione IRCCS Cà Granda (Milan), and other centers that may later join the study.

#### - Baseline visit and informed consent

The Investigator will invite patients to participate after verifying inclusion/exclusion criteria. Patients (or legal representatives in case of cognitive impairment) will receive detailed information on study aims, benefits, and potential risks, along with written information sheets and informed consent forms. Adequate time will be allowed for discussion with the general practitioner before consent. Patients will also be asked whether they agree to be re-contacted for future research studies.

Investigators at the Genoa and Milan centers are responsible for obtaining and archiving signed informed consent before any study-specific procedures.

#### - Visit 1

At this visit, informed consent will be obtained, and subjects will be enrolled with assignment of a pseudonymized code generated in REDCap using the Mainzelliste algorithm (PMID: 25656224). The algorithm processes identifying attributes (e.g., name, surname, date of birth) to generate a unique, anonymous personal identifier (PID), ensuring record linkage across multiple databases while tolerating spelling variations.

Peripheral blood (20–25 mL) will be collected for preparation of PBMCs, serum, and/or plasma, and urine will be collected for omics analyses. DNA will be extracted from whole blood, RNA preferably from PBMCs; saliva may be used as an alternative genetic source. Sampling will be integrated into routine clinical workflow.

Clinical and biological data will be collected at IRCCS Policlinico San Martino ([name]), Fondazione IRCCS Cà Granda ([name] [name]), and other participating centers.

#### Clinical data collection

Following consent, clinical data will be collected at participating Units and managed through REDCap. Case report forms (CRFs) will specify disease-specific data. At Visit 1, the following will be recorded:

- Sex
- Age
- Medical history
- Neurological examination
- Neuropsychological profile
- Neuroimaging findings
- Previous treatments
- Planned treatments

#### - Visit 2

If consent is given, patients/legal representatives will be informed of clinically relevant genetic variants identified. Variants associated with risk of developing other conditions (subject to confirmatory testing) will be disclosed during genetic counseling with psychological support. Patients will also decide whether information should be extended to relatives.

#### - Follow-up visits

Subsequent follow-up visits will coincide with routine clinical visits in Neurology and Geriatrics Units at Genoa and Milan centers.

## 7.2 Sample Collection and Processing

### - Genomic data collection

Molecular and genetic diagnostic data generated at Genoa and Milan centers will be entered into the CRF and REDCap. Genomic data generated by IIT-CMP3VdA will be stored at the Engineering D.Hub data center in Pont Saint Martin (Aosta), with backup in Vicenza.

### - Biological sample processing

Samples will be collected at Neurology and Geriatrics Units of IRCCS Policlinico San Martino ([name]) and Fondazione IRCCS Cà Granda ([name] [name]), frozen, and stored in local biobanks (Genoa Biobank; Telethon Biobank, Milan). DNA/RNA will be extracted from PBMCs and/or peripheral blood and derivatives according to omics analyses to be performed at the respective hospital laboratories. Part of the pseudonymized DNA/RNA sample will be transferred to IIT (Genoa and Aosta CMP3VdA) for subsequent genomic analyses.

### - Biobanking

#### Serum and plasma isolation

Serum and plasma isolation will be performed following standard procedures: blood samples will be collected in dedicated tubes (K2/K3 EDTA for plasma and clot activator for serum and/or with stabilization solutions for nucleic acids) and centrifuged once or multiple times (ranging from 1600 to 3000g) at room temperature and/or +4°C, depending on whether serum or plasma is being prepared. Cryovials containing aliquots of serum and plasma will be stored at -80°C.

#### PBMC collection and culture

Two EDTA or Lithium-Heparin tubes will be layered onto Ficoll and centrifuged at 2000g for 20 minutes to obtain the PBMC fraction, which will be isolated and frozen in FBS + 10% DMSO at -80°C.

#### Biomarkers

Biomarkers will be analyzed using standardized methodologies. For biomarkers already assessed in clinical practice, values will be retrieved from the patients' medical records. Should new diagnostic biomarkers become available over time, these will also be analyzed according to validated and standardized procedures.

### - Sequencing

NGS sequencing will be performed in collaboration with IIT using state-of-the-art sequencing technologies. The laboratory is equipped with both second- and third-generation sequencing platforms, enabling short- and long-read sequencing, respectively, with the possibility of integrating both technologies when advantageous for research purposes.

Short-read Illumina sequencing allows highly accurate analysis of single-nucleotide variants (SNVs) and small insertions/deletions (indels), while long-read sequencing facilitates the analysis and identification of structural variants (SVs). These NGS platforms represent the state of the art for transcriptomic (RNA-Seq), epigenomic, and metagenomic studies.

The **Illumina NovaSeq 6000**, currently available at Fondazione Istituto Italiano di Tecnologia in Genoa and Aosta (CMP3VdA), ensures high throughput, generating up to 6 terabases of sequencing and 20 billion reads per run. Sequencing quality is high, with over 75% of bases reaching a quality score  $\geq 30$ . Sequencing outputs FASTQ files stored directly in the cluster's analysis storage. A minimum sequencing depth of 30X will be applied, enabling comprehensive variant identification, classification, and association with neurodegenerative diseases.

The **PromethION 24 system** (Oxford Nanopore Technologies, ONT), also available at CMP3VdA, provides flexible, ultra-high throughput third-generation sequencing, with 24 independent flow cells generating terabases of data in real time. This technology enables direct sequencing of native DNA/RNA strands using nanopores embedded in an electro-resistant membrane, through which ionic current alterations induced by nucleic acid passage are converted into genomic sequences via basecalling software.

Third-generation sequencers, due to their ability to process long fragments, offer superior resolution in detecting short repeat units (<1 kb), repeat-rich DNA regions, and large-scale inversions (>10 kb), while also allowing haplotype phasing and improved resolution of compound heterozygosity. Sequencing depth typically ranges between 2–5X, depending on the study design.

